#### **4.2.8.3 Sub-study explorative analysis**

Only descriptive statistics for SGaw and Raw and change from baseline will be provided at each scheduled visit at which assessments are performed.

Subgroup analyses of RV and ratio TLC/RV may be performed for the age group categories (18-30 years, 31-65 years).

#### **4.2.9 Safety outcome variables**

All safety variables will be summarized using the safety analysis set and data presented according to actual treatment received.

##### **4.2.9.1 Adverse events**

Adverse events (AEs) will be summarized for the on-study period, as defined in Section 3.5.1. All summaries will be presented by treatment group.

An overall summary table will be produced showing the number and percentage of patients with at least 1 AE in any of the following categories: AEs, serious adverse events (SAEs), AEs with outcome of death, and AEs leading to discontinuation of IP (DAEs). The total number of AEs in the different AE categories in terms of AE counts will also be presented (ie, accounting for multiple occurrences of the same event in a patient).

Adverse events, AEs with outcome of death, and SAEs will be summarized by SOC and PT assigned to the event by MedDRA. For each PT, the number and percentage of patients reporting at least 1 occurrence will be presented (ie, multiple occurrences of an AE for a patient will only be counted once). Adverse events causing discontinuation of the study treatment and SAEs causing discontinuation from the study will also be summarized.

The rate of AEs per person-years at risk, calculated as (number of patients reporting AE)/(total period with patients at risk for AE), will also be reported. The total period at risk for each patient will be defined as the period from first dose of study treatment to the follow-up visit (Week 16). Rates will be expressed in terms of events per 100 patient-years.

A summary of the most common (frequency of  $\geq 5\%$ ) AEs will be presented by PT. Adverse events will be summarized by PT and Investigator's causality assessment (related versus not related) and maximum intensity. If a patient reports multiple occurrences of the same AE within the same study period, the maximum intensity will be taken as the highest recorded maximum intensity (the order being mild, moderate, and severe). Adverse events of injection site reactions (high-level term of administration and injection site) and hypersensitivity (standardized MedDRA query of hypersensitivity) will be summarized by PT. The summary of injection site reactions will be summarized by injection site location and number of IP administrations.

Adverse events related to device malfunction will be listed. All adverse events will be listed.

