6.3.3 Variables

The following variables will be collect for each AE;

- AE (verbatim)
- The date when the AE started and stopped
- Maximum intensity of the AE
- Whether the AE is serious or not
- Investigator causality rating against the Investigational Product (yes or no)
- Action taken with regard to investigational product
- AE caused subject's withdrawal from study (yes or no)
- Outcome.

In addition, the following variables will be collected for SAEs:

- Date AE met criteria for serious AE
- Date Investigator became aware of serious AE
- AE is serious due to
- Date of hospitalization

- Date of discharge
- Probable cause of death
- Date of death
- Autopsy performed
- Causality assessment in relation to Study procedure(s)
- Description of AE

It is important to distinguish between serious and severe AEs. Severity is a measure of intensity whereas seriousness is defined by the criteria in Section 6.2. An AE of severe intensity need not necessarily be considered serious. For example, nausea that persists for several hours may be considered severe nausea, but not a SAE unless it meets the criteria shown in Section 6.2. On the other hand, a stroke that results in only a limited degree of disability may be considered a mild stroke but would be a SAE when it satisfies the criteria shown in Section 6.2.

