6.3.8 Disease progression

When collecting AEs, the recording of diagnoses is preferred, when possible, to recording a list of signs and symptoms. Asthma symptoms or signs, such as wheeze, cough, chest tightness, dyspnea, breathlessness and phlegm, will be recorded as AEs only when:

- The sign or symptom is serious according to definitions, see Section [6.1](#)
- The patient discontinues the study due to the sign or symptom
- The sign or symptom is new to the patient or not consistent with the patient's pre-existing asthma history (defined as within 1 year of Visit 1) as judged by the Investigator.

Asthma exacerbation should be recorded as an AE or SAE only if it fulfills any of the above criteria.

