8.5.2.3 Analysis of the safety variables

Adverse events will be coded using the MedDRA dictionary. Number of subjects with events and percentages will be tabulated by preferred term and system organ class. An event that occurred once or more times during the study treatment period will contribute 1 observation to the numerator of the proportion. The denominator of the proportion will comprise all subjects in the Safety set. Adverse events will also be summarized by intensity/severity and separately, by causality/relatedness (as determined by the investigator). Should a subject report the same preferred term/system organ class within multiple intensity/severity or causality/relatedness categories, the subject's worst occurrence (most severe/most related) will be tabulated. Serious AEs, AEs leading to discontinuation, and commonly occurring AEs will be summarized in a generally similar manner. Adverse events, SAEs, AEs leading to death, and AEs leading to study discontinuation will be summarized for each treatment group as applicable.

Laboratory data will be summarized by presenting shift tables using normal ranges (baseline to most extreme post-baseline value) and by presenting summary statistics of observed and change from baseline values (means, medians, quartiles, ranges). The incidence of clinically notable lab abnormalities will be summarized.

Vital sign data will be summarized by presenting summary statistics of observed and change from baseline values. The incidence of clinically notable vital sign abnormalities will be summarized.

Electrocardiogram intervals will be summarized by presenting summary statistics of observed and change from baseline values. The (uncorrected) QT interval will be corrected according to the Fridericia's formula. The incidence of clinically notable ECG abnormalities will be summarized.

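### SAP 4.2.9.1 limits the summary of events leading to study discontinuation to SAEs, whereas protocol 8.5.2.3 covers all AEs, and SAP section 6 does not record the change

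*SAP*

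**What the plan says.** Protocol 8.5.2.3 (Analysis of the safety variables) states: "Adverse events, SAEs, AEs leading to death, and AEs leading to study discontinuation will be summarized for each treatment group as applicable". SAEs are named separately in that sentence, so AEs there means all AEs. The same section says that AEs leading to discontinuation are handled much like the general AE tables, which are by preferred term and system organ class.

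SAP 4.2.9.1 (Adverse events) plans a summary of the AEs that stopped study treatment. For leaving the study, the same sentence says only: "SAEs causing discontinuation from the study will also be summarized". All AEs are in scope for stopping treatment, but only serious ones for leaving the study. The SAP's overall AE table has categories for any AE, SAEs, deaths and AEs that stopped IP. It has none for AEs that led to study withdrawal.

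Protocol 6.3.3 collects, for every AE, the action taken with IP and, as a separate yes/no item, whether the AE caused withdrawal from the study. Protocol 6.3.8 lists the circumstances in which asthma signs and symptoms count as AEs. One is: "The patient discontinues the study due to the sign or symptom".

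SAP section 6 records one change from the protocol, the dropping of ECG interval summaries. It cites protocol 8.5.2.3 for that change and does not mention the AE summary. The SAP amendment history does not mention it either.

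**The concern.** The SAP delivers less than the protocol promised for a safety output, and gives no reason and no record of the change. Stopping IP and leaving the study are separate events in this trial. Protocol 3.10.1 encourages patients who stop IP to stay for the remaining visits, and SAP 4.2.1 counts those who stopped IP but completed follow-up separately from those who withdrew. The summary of AEs that stopped IP therefore cannot stand in fully for a summary of AEs that ended participation.

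At stake is part of the tolerability picture: which non-serious events made patients leave, and whether they differ between arms. The asthma rule in protocol 6.3.8 sharpens this. A non-serious worsening may be recorded as an AE only because the patient left, yet no planned summary would show that it caused the departure.

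**Working it through.** No sample size, power or error rate is involved, so there is nothing to recompute. The check is to set the planned outputs side by side and see what each shows for a non-serious AE that causes study withdrawal.

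| Planned output | Includes the event or patient? | Names the event? | Shows that it caused withdrawal? |
|---|---|---|---|
| Protocol 8.5.2.3, AEs leading to study discontinuation | Yes | Yes, if done like the other AE tables | Yes |
| SAP 4.2.9.1, SAEs causing study discontinuation | No, serious only | – | – |
| SAP 4.2.9.1, AEs causing discontinuation of treatment | Only if IP was also stopped for it | Yes | No, shows the IP stop |
| SAP 4.2.9.1, on-study AEs by class and term | Yes | Yes | No |
| SAP 4.2.1 disposition and Appendix 8.1 withdrawal reasons | Patient counted under the reason | No | Yes, as a category |
| SAP 4.2.9.1, listing of all AEs | Yes | Yes | Not stated; a listing is not a summary |

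The SAP tables in rows 2 to 5 are by arm. For the AE tables the SAP says: "All summaries will be presented by treatment group". Disposition and withdrawal reasons are also given by treatment.

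Next, when does the event escape the IP-discontinuation summary?

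1. While doses remain. Protocol 3.10.1 describes withdrawal from the study as covering both IP and assessments. A patient who leaves because of an AE before the last dose therefore also stops IP, and the AE belongs in the by-arm IP-discontinuation summary.
2. After the last planned dose. Dosing is at Days 0, 28 and 56, and AEs are collected through Day 112. That leaves 112 − 56 = 56 days, half of the 112 days after randomization, with no planned dose left to stop. A non-serious AE causing withdrawal here would not naturally be recorded as stopping IP.
3. After an earlier IP stop for another reason. A patient who stopped IP, stayed in the study and later left because of a non-serious AE is in the same position.

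Routes 2 and 3 make up the gap.

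Finally, the link to the primary analysis. The primary model uses FEV₁ up to Day 84. Of the 56 days after the last dose, the first 84 − 56 = 28 can cost a patient the Day 84 value. The remaining 112 − 84 = 28 cannot affect the primary analysis. For withdrawals before Day 84, the dropout-reason-based imputation in Appendix 8.1 works from the withdrawal-reason category. It uses neither the preferred term nor the seriousness of the AE, so the missing table changes no estimate.

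**The case against.** The strongest reply is that little is lost. Withdrawals for adverse events are counted by arm, serious and non-serious together. AEs that stopped IP are summarised by arm, every on-study AE is tabulated by class, term and arm, and all AEs are listed. The protocol's sentence also ends with an as-applicable qualifier.

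Most of this stands. A reader might infer from the SAP sentence that non-serious AEs behind withdrawals are never tabulated by arm. The documents do not support that: the patients, and separately the events, do appear in by-arm tables. What those tables lack is the link between the named event and the withdrawal.

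A reader might also infer that the gap undermines the missing-data analysis, because benralizumab patients withdrawn for an adverse event are imputed from placebo. That is not supported either. The imputation needs only the reason category, which is tabulated by arm. Seeing the events would help a reader judge the assumption, but it would alter nothing in the analysis.

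The qualifier does not rescue the SAP. It is a general hedge and does not turn AEs into SAEs in a sentence that names both.

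**Conclusion.** The SAP is wrong as written against protocol 8.5.2.3, and the departure is undeclared. The consequence is limited: non-serious AEs that led to study withdrawal without IP discontinuation are not identified by term and arm as the cause. These arise mainly between Day 56 and Day 112 and include asthma worsening recorded as an AE because the patient left. The documents give no basis for estimating how many there will be; there may be none.

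This rests on two assumptions: that an AE starting after the last planned dose is not recorded as having stopped IP, and that the protocol's summary was meant to be by term, like its other AE tables. Severity is minor. The primary analysis, its error rate and its imputation rules are untouched.

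**What to change.** In SAP 4.2.9.1, change the clause on study discontinuation so that it covers AEs (serious and non-serious) causing discontinuation from the study. Summarise them by system organ class, preferred term and treatment group, with SAEs shown as a subset. Derive the table from the AE-level withdrawal item in protocol 6.3.3.

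If the sponsor prefers to keep the restriction, it should at least be entered in SAP section 6 with a reason, next to the ECG change from the same protocol section.

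The cost is a small wording change and one descriptive table. No new data are needed.

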## 1.2 Study design

This is a randomized, double-blind, parallel group, placebo-controlled study designed to evaluate the onset of effect and safety of a fixed 30 mg dose of benralizumab administered subcutaneously (SC) to patients with severe, uncontrolled asthma. Approximately 230 patients with peripheral blood eosinophil counts  $\geq 300$  cells/ $\mu$ L will be randomized globally to receive SC benralizumab 30 mg or placebo.

After enrolment, eligible patients will enter a 5-week screening/run-in period. Patients who meet eligibility criteria will enter a 12-week treatment period and receive 30 mg benralizumab or placebo at Day 0, Day 28 (+/- 3 days), and Day 56 (+/- 3 days). An End-of-Treatment (EOT) visit will be conducted at Day 84 (Week 12) and a follow-up (FU) visit will be conducted at Day 112 (Week 16).

See the clinical study protocol (CSP) Section 4, Tables 2 and 3 for a detailed list of visits and assessments.

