## 1.3 Number of subjects

The study will recruit approximately 230 patients in total and 115 patients in each treatment group based on the primary objective of the study to determine the effect of benralizumab on the time course of change (onset and maintenance of effect) of pre-bronchodilator (BD) FEV1.

Patients will be randomized in a 1:1 ratio to benralizumab or placebo. In order to have a balanced number of patients for each region and the body plethysmography sub-study, the randomization will be stratified by these variables.

The study is powered for the primary objective of the study to determine the effect of benralizumab on the time course of change (onset and maintenance of effect) of pre-BD FEV1.

The first post-baseline timepoint where the p-value for the mean difference between benralizumab and placebo is  $\leq 0.05$  will be used to determine time to onset of effect. The average over the mean differences between benralizumab and placebo based on the change from baseline (Visit 4) to Days 28 (Visit 8), 56 (Visit 9), and 84 (Visit 10) in pre-BD FEV1 will be used to determine if the study is positive and to determine maintenance of effect.

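### The adverse event rate counts patients over full follow-up to Week 16 but is labelled as events per 100 patient-years, so its definition and its label do not match

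*SAP*

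**What the plan says.** Three consecutive statements in SAP section 4.2.9.1 define the rate.

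- Numerator and denominator: "calculated as (number of patients reporting AE)/(total period with patients at risk for AE), will also be reported".
- Time at risk: "The total period at risk for each patient will be defined as the period from first dose of study treatment to the follow-up visit", which the SAP places at Week 16.
- Label: "Rates will be expressed in terms of events per 100 patient-years".

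The same section handles patients and events separately elsewhere. In the preferred-term (PT) tables, "multiple occurrences of an AE for a patient will only be counted once". For the overall summary, "The total number of AEs in the different AE categories in terms of AE counts will also be presented", by AE category. Those counts do not enter the rate.

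SAP section 1.2 puts the follow-up visit at Day 112 (Week 16). SAP section 4.1 ends the safety period at the same visit but calls it Week 11. Protocol section 8.5.2.3 plans only proportions for AEs and gives no other rate definition, and SAP section 6 (changes from protocol) does not mention the rate.

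**The concern.** Two person-time rates are in common use. A first-event rate counts each patient once and ends that patient's time at risk at the first event. An event rate counts every occurrence over all follow-up time. The SAP takes the numerator of the first and the denominator and label of the second.

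The mention of time with patients at risk could suggest that time stops at the first event, but the next sentence defines the period without such a stop. Nor can the numerator be read as events, since the section defines AE counts separately.

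What is at stake is how the clinical study report is read. Someone who takes the label at face value will think the figure reflects how often events occur. Among patients with full follow-up it carries no information on timing or recurrence beyond the percentage of patients affected.

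**Working it through.** The documents state no AE rate and assume no AE frequency, so there is no plan figure to reproduce.

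**Inputs from the documents**
- Follow-up per completing patient: Day 112 (SAP section 1.2), so T = 112/365.25 = 0.3066 years.
- Scale: "115 patients in each treatment group" (SAP section 1.3), which gives 115 × 0.3066 = 35.3 patient-years per arm with full follow-up.
- Threshold for common AEs: 5% of patients (SAP section 4.2.9.1).

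**Assumptions**
- p, the share of patients with the AE by Week 16: 5%, 20% and 50%.
- No dropout.
- Onset pattern of first events: constant hazard, or spread evenly over the first 28 days (mean day 14), or over the last 28 days (mean day 98).
- m, the mean number of events per affected patient: 1, 1.5 and 2.

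**Step 1. The plan's rate.** Rate = 100 × p / T. With p = 100% this is 100/0.3066 = 326.1 per 100 patient-years, a ceiling that holds however many events occur. With p = 20%, 23 of 115 patients over 35.3 patient-years give 65.2.

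**Step 2. First-event rate under constant hazard.** Rate = 100 × (−ln(1 − p)) / T. With p = 20%: 100 × 0.2231/0.3066 = 72.8, so the plan's figure is 1 − 65.2/72.8 = 10.4% lower.

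**Step 3. Other onset patterns.** If affected patients have their first event on day *a* on average, mean time at risk is p × a + (1 − p) × 112 days. The plan's shortfall is then p × (112 − a)/112, which is 0.875p for early onset (a = 14) and 0.125p for late onset (a = 98).

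| Patients affected | Plan's rate per 100 PY | First-event rate, constant hazard | Shortfall, constant hazard | Shortfall, early onset | Shortfall, late onset |
|---|---|---|---|---|---|
| 5% | 16.3 | 16.7 | 2.5% | 4.4% | 0.6% |
| 20% | 65.2 | 72.8 | 10.4% | 17.5% | 2.5% |
| 50% | 163.1 | 226.0 | 27.9% | 43.8% | 6.3% |

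**Step 4. Event rate.** Rate = 100 × p × m / T, so the plan's figure is the event rate divided by m, whatever p is. The shortfall is 1 − 1/m: zero at m = 1, 33% at m = 1.5 and 50% at m = 2.

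**Step 5. End of follow-up.** SAP section 4.1 gives Week 11 for the follow-up visit; SAP sections 1.2 and 4.2.9.1 give Week 16. The SAP also does not say what time at risk a patient contributes who leaves before Week 16. Protocol section 3.10.1 allows such patients: someone who stops treatment and declines further visits has a final visit 8 weeks after the last dose.

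**The case against.** The best defence is that patients over total follow-up time is a simple exposure-scaled summary. It is too low only against a hazard or an all-events rate, and the SAP does not claim to estimate a hazard. For completers it is the incidence proportion divided by a constant, and the same section already gives percentages by PT, AE counts by category and a listing of all AEs. This stands as a limit on the consequences. It does not rescue the label: a count of patients is not a count of events.

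The sizes also rest on hypothetical frequencies. Protocol sections 6.3.6 and 6.3.8 restrict when asthma symptoms and laboratory or vital-sign changes are recorded as AEs, so frequencies near 50% are most plausible for the row for any AE. Near the 5% threshold the gap is small, and against an event rate it is zero if nobody has a repeat. This stands too.

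A reader might infer that the rule pulls a true difference between arms toward equality. If 60% and 40% of the arms had an AE, the plan's ratio would be 40/60 = 0.67, and the first-event ratio under constant hazard ln(0.60)/ln(0.40) = 0.56. But 0.67 is simply the risk ratio that the percentage tables already show. The two numbers are different measures, not a biased and a correct version of one. The SAP plans no between-arm AE test or rate ratio, so no planned inference is distorted.

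**Conclusion.** The definition and label in SAP section 4.2.9.1 are inconsistent, and nothing elsewhere in the documents repairs them. With full follow-up the reported figure is the percentage affected rescaled by 0.3066 years and capped at about 326 per 100 patient-years. The gap to a first-event rate is minor for most individual terms and material for frequent ones; the gap to an event rate depends entirely on repeat events. Only the ceiling and the rescaling follow from the documents alone, given full follow-up. The percentage gaps depend on assumed frequencies, onset patterns and numbers of repeats.

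The documents do not support reading this as a general bias in the safety results. It concerns one supplementary descriptive statistic for the clinical study report. It should be corrected because readers will take the label literally and the correction is easy.

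**What to change.** Choose one of two definitions and state it in SAP section 4.2.9.1.

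- **(a) First-event rate.** Keep the patient numerator. End each patient's time at the first occurrence of the AE being tabulated, or at actual last follow-up if that is earlier. Label it as patients with event per 100 patient-years at risk.
- **(b) Event rate.** Count all occurrences at the level being tabulated, including by PT, over each patient's actual follow-up, and keep the present label. The AE counts planned for the overall summary are by category only, so PT-level counts would have to be produced.

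Either choice also settles the time contributed by patients who leave before Week 16. Separately, reconcile Week 11 in SAP section 4.1 with Week 16 in sections 1.2 and 4.2.9.1.

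The cost is about one sentence on the rate, one corrected week number and a small programming change. No new data are needed: AE onset dates and visit dates are already collected.
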